An Investigator Initiated Study of Monocyte Biomarkers in Moderate to Severe Plaque Psoriasis Subjects Treated with Apremilast

INVESTIGATIONAL PRODUCT (IP): Apremilast

**PROTOCOL NUMBER: UH IRB# 07-17-33
Amgen study 20207105**

VERSION: 8.0 Date: 27May2021

SPONSOR NAME / ADDRESS:

**[name]
University Hospitals Cleveland Medical Center (UHCMC)
Department of Dermatology
[name]
[name]**

MEDICAL MONITOR / EMERGENCY CONTACT INFORMATION

Contact Information:	
Name:	[name], PhD
Title:	Director, Clinical Trials Unit
Address:	University Hospitals Cleveland Medical Center Department of Dermatology [name]
[contact]
E-mail:	[contact]

PROTOCOL SUMMARY

Study Title

Otezla Reversal of Psoriasis Aberrant Monocyte CVD Event-Risk Biomarkers

Indication

Psoriasis is a chronic disease that requires long-term treatment, ideally with effective agents that offer convenient dosing and a low incidence of adverse events. Currently available systemic therapies are limited by risks of hepatic, renal and neurological toxicities, teratogenicity, as well as an increased risk of infections and malignancies. Most biologic therapies designed to treat psoriasis are administered parenterally. Given the limitations of current systemic psoriasis treatments, there is an unmet medical need for an effective oral agent that is well tolerated and less immunosuppressive than the current oral agents and parenteral biologics.

Apremilast (Otezla) is a specific phosphodiesterase type 4 (PDE4) inhibitor used in the treatment of inflammatory conditions. PDE4 is one of the major phosphodiesterases expressed in leukocytes. Inhibitors of PDE4 cause accumulation of intracellular cyclic adenosine monophosphate (cAMP), resulting in inhibition of pro-inflammatory cytokine transcription and other cellular responses, such as neutrophil degranulation and chemotaxis.

Apremilast has demonstrated broad anti-inflammatory and immunomodulatory activity, as well as efficacy in psoriasis and psoriatic arthritis. Based on preclinical and clinical data to date, apremilast has a more favorable safety profile than the currently available systemic psoriasis treatments, while delivering efficacy with convenient oral dosing.

Objectives

Primary Objective

- Evaluate aberrant inflammatory profiles of activated blood monocytes known as the aberrant-monocyte endotype (i.e. AM-endotype)
- Assess the median reduction of abnormal monocyte biomarker values in AM-endotype patients treated with oral apremilast (Otezla) under recommended dosing:
 - Day 1: 10 mg in morning
 - Day 2: 10 mg in morning and 10 mg in evening
 - Day 3: 10 mg in morning and 20 mg in evening
 - Day 4: 20 mg in morning and 20 mg in evening
 - Day 5: 20 mg in morning and 30 mg in evening
 - Day 6 - Day 112: 30 mg twice daily

Secondary Objectives

- Evaluate the median change in serum myeloperoxidase, resistin, IL-17, and Tissue Factor in the AM-endotype.
- Evaluate the median change in flow cytometric quantitation of additional monocyte and neutrophil markers, including CD18/CD11b and NETotic neutrophils.
- Evaluate change in monocyte transcriptome biomarkers by WGS.

Other Objective(s)

[figure not shown]
- Evaluate Health Related Quality of Life (HRQoL) (Dermatology Life Quality Index (DLQI) and (Work Productivity and Activity Impairment Questionnaire: Psoriasis (WPAI: PSO)) and changes in symptom severity of patients receiving apremilast 30 mg BID.
- Explore potential change in Framingham Risk profile of treated patients.

Study Design

This is an open label pilot study of the impact of treatment with standard dosing of APM for 16 weeks on AM-endotype psoriasis patients, identified by elevated (>150% of normal):

1. Intermediate (CD14⁺⁺CD16⁺) monocytes (i.e. monocytes in circulation), OR
2. Circulating monocyte doublets (i.e. adherent monocyte-monocyte pairs), OR
3. Circulating monocyte-platelet aggregates (i.e. monocytes adherent to platelets; MPA).

Study Design

Approximately 25 psoriasis patients with the AM-endotype will be followed during treatment over 16 weeks with 5 monthly individual blood draws will be enrolled. 10 untreated healthy controls will also be enrolled and will provide two blood draws (baseline and 16 weeks). These are needed to maintain quality control of the normal levels of the biomarkers being tested. All treated psoriasis subjects will receive apremilast through Week 16

Study Population

Adult subjects 18-65 years of age with moderate-to-severe plaque psoriasis.

Healthy controls

Healthy participants will be recruited from a pool of generally healthy research volunteers. Healthy volunteers will be selected to match age, sex, and race of psoriasis subjects as closely as possible.

Length of Study

The study is designed as a 16 week study and consists of 6 distinct visits as described above. Screening will consist of a 1a and optional 1b visit. Visit 1b is optional. It exists so that the subject can pick up the Empatica E4 wrist device that cannot be given until their monocyte profile is known. Visits 3 and 5 will also be split into part a and b. Visit b will be optional. If the subject chooses to participate, visit b is when the subject returns the wrist device.

Study Treatments

Apremilast will be dispensed in dose titration cards at Visit 2. At Visit 3, apremilast tablets will be supplied in high density polyethylene (HDPE) bottles containing approximately 60 tablets each.

Overview of Efficacy Assessments

Primary Clinical Assessment

The primary clinical assessment will be Psoriasis Area and Severity Index (PASI) scores.

Additional Clinical Assessments

- Static Physician's Global Assessment (sPGA)
- Body Surface Area (BSA)
- Subject's Assessment of Pruritus VAS
- Subject's Assessment of Skin Discomfort/Pain VAS
- Subject Global Assessment of Psoriasis Disease Activity VAS
- Subject's Assessment of Joint Pain VAS
- Subject Global Assessment of Psoriatic Arthritis Disease Activity VAS
- Health Related Quality of Life (HRQoL) questionnaires:
 - Dermatology Life Quality Index (DLQI)
 - Work Productivity and Activity Impairment Questionnaire: Psoriasis (WPAI: PSO)

Overview of Safety Assessments

Safety Assessments

- Adverse events (AE)
- Physical examinations
- Vital signs
- Clinical laboratory tests
- Evaluation of psoriasis flare or rebound.

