1.4. Rationale for Dose Chosen

Apremilast

Apremilast will be given as approved by the FDA for the treatment of moderate-to-severe plaque psoriasis. An initial dosage titration from Day 1 to Day 5 will be performed as shown below:

Dosing titration schedule for week 1									
Day 1		Day 2		Day 3		Day 4		Day 5+	
am	pm	am	pm	am	pm	am	pm	am	pm
10mg	x	10mg	20mg	20mg	20mg	20mg	30mg	30mg	30mg

Following the titration, the recommended maintenance dosage of 30 mg twice daily taken orally will be continued throughout the study.

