7. DESCRIPTION OF STUDY TREATMENTS

7.1. Description of Investigational Product(s)

7.1.1. Description of Apremilast

The chemical name of apremilast (CC-10004, Otezla) is acetamide, N-[2-[(1S)-1-(3-ethoxy-4-methoxyphenyl)-2-(methylsulfonyl)ethyl]-2,3-dihydro-1,3-dioxo-1H-isoindol-4-yl].

Apremilast will be provided as 10, 20, or 30 mg tablets in blister cards for titration purposes (see Appendix N). Apremilast will be provided as 30 mg tablets in HDPE bottles (approximately 60tablets) with child-resistant caps for routine dosing.

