7.1.2 Treatment Administration and Schedule

Apremilast

Investigational product tablets will be taken orally twice daily, approximately 12 hours apart, without restriction of food or drink. To attempt to mitigate potential mild to moderate headache and gastrointestinal (GI) adverse events (primarily nausea), dose titration will be implemented in this study at specific times.

Dosing

During Week 0 (Days 1-7), subjects will be dispensed blister cards with standardized dosing of apremilast tablets.

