7.1.5. Investigational Product Compliance

Study personnel will review the instructions printed on the package with the study subjects prior to dispensing Otezla. The subjects will be instructed to return the Otezla containers, including any unused medication, to the study site at each visit for tablet counts and reconciliation. Subjects will be asked whether they have taken their Otezla as instructed at each study visit and will be required to complete a medication log at home that will be returned at study visits 3-6. Any problems with compliance will be reviewed with the subject.

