Appendix G: Blister Card Configuration

CC-10004-PSOR-010 30m

CC-10004-PSOR-010 30mg Titration Card Week 16 (7 day +4 Extra)

	1	10P		20p	30		1	10P		20p	30
	2	10P		20p	30		2	10P		20p	30
	3	10P		20p	30		3	10P		20p	30
	4			20p	30		4			20p	30
	5			20p	30		5			20p	30
	6			20p	30		6			20p	30
	7			20p	30		7			20p	30
	8			20p	30		8			20p	30
	9			20p	30		9			20p	30
	10			20p	30		10			20p	30
	11			20p	30		11			20p	30

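### The protocol gives two different first-week apremilast titration schedules, and nothing else in it says which one applies

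*Combined protocol and SAP*

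**What the plan says.** The Protocol Summary sets out the dosing day by day under the primary objective. It starts with "Day 1: 10 mg in morning" and no evening dose, then "Day 2: 10 mg in morning and 10 mg in evening". Days 3, 4 and 5 follow at 10/20, 20/20 and 20/30 mg (morning/evening), and then "Day 6 - Day 112: 30 mg twice daily".

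Section 1.4 (Rationale for Dose Chosen) states "An initial dosage titration from Day 1 to Day 5 will be performed as shown below". The table beneath gives 10 mg in the morning only on Day 1, then 10/20, 20/20 and 20/30 mg on Days 2 to 4, and 30/30 mg in a column headed Day 5+.

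The other places where one would look for the schedule are these:

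- **Summary (Study Treatments) and Section 4 (Table of Events):** titration cards are dispensed at Visit 2, with no doses given.
- **Section 7.1.1:** "tablets in blister cards for titration purposes (see Appendix N", but the appendices in the document run from A to G.
- **Section 7.1.2:** for Days 1-7, "subjects will be dispensed blister cards with standardized dosing of apremilast tablets", with no daily amounts.
- **Section 7.1.3:** the label carries dosing instructions, which are not reproduced. It also says that all apremilast comes in bottles, which does not fit the blister cards described elsewhere.
- **Section 7.1.5:** "Study personnel will review the instructions printed on the package with the study subjects prior to dispensing Otezla".
- **Appendix G:** a card page headed "CC-10004-PSOR-010 30mg Titration Card Week 16 (7 day +4 Extra".

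**The concern.** Both schedules are current Version 8.0 text, and they give different doses of the study drug for the same days. The Section 1.4 table is complete as extracted (five day headings, ten morning/evening columns, ten entries), so the conflict does not come from a damaged table. Section 1.4 is also at odds with itself: its sentence describes a titration lasting through Day 5, while its table is already at the maintenance dose on Day 5.

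Section 7.1.2 describes titration as an attempt to mitigate possible mild to moderate headache and gastrointestinal events, mainly nausea. The first-week instruction therefore has a stated purpose and needs a single reading.

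The protocol also attaches consequences to departures from dosing. Section 9.3 tabulates deviations, Section 10.1 makes an overdose reportable as an adverse event, and Section 11 lists non-compliance and protocol violation as grounds for discontinuation. For Days 2 to 5 the protocol supplies two reference doses for applying those rules.

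Unequal exposure between subjects is a risk, not something the documents show. If every card followed one layout, exposure would be uniform, but that layout would still contradict one protocol page on four days.

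**Working it through.** The plan states no total for the titration, so there is no figure of its own to reproduce. The inputs are the daily doses in the Summary and in the Section 1.4 table. The column Day 5+ is read as Day 5 and every later day.

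**Step 1. Daily doses (morning/evening, mg)**

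| Day | Summary | Total | Section 1.4 | Total | Difference |
|---|---|---|---|---|---|
| 1 | 10/none | 10 | 10/none | 10 | 0 |
| 2 | 10/10 | 20 | 10/20 | 30 | 10 |
| 3 | 10/20 | 30 | 20/20 | 40 | 10 |
| 4 | 20/20 | 40 | 20/30 | 50 | 10 |
| 5 | 20/30 | 50 | 30/30 | 60 | 10 |
| 6 | 30/30 | 60 | 30/30 | 60 | 0 |
| 7 | 30/30 | 60 | 30/30 | 60 | 0 |

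The schedules differ on four days, and the total difference is 4 × 10 = 40 mg.

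**Step 2. Cumulative prescribed dose, Summary against Section 1.4**

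- Days 1-5: 10+20+30+40+50 = 150 mg; 10+30+40+50+60 = 190 mg; 40/150 = 26.7%.
- Days 1-7: 150 + 2×60 = 270 mg; 190 + 2×60 = 310 mg; 40/270 = 14.8%.
- Days 1-28: 150 + 23×60 = 1530 mg; 190 + 23×60 = 1570 mg; 40/1530 = 2.6%.
- Days 1-112: 150 + 107×60 = 6570 mg; 190 + 107×60 = 6610 mg; 40/6570 = 0.6%.

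**Step 3. Tablets needed for Days 1-7, assuming one tablet per dose**

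| Strength | Summary | Section 1.4 |
|---|---|---|
| 10 mg | 4 | 2 |
| 20 mg | 4 | 4 |
| 30 mg | 5 | 7 |
| Total | 13 | 13 |

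Check: 4×10 + 4×20 + 5×30 = 270 mg and 2×10 + 4×20 + 7×30 = 310 mg, matching Step 2. The total count is the same but the mix is not. One exact card cannot serve both schedules, and a count of tablets without regard to strength would not show which had been followed.

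**Step 4. Search for a tie-breaker**

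Sections 7.1.1, 7.1.2, 7.1.3 and 7.1.5, the Study Treatments paragraph of the Summary and the Table of Events contain no daily doses. The references to recommended, standard or FDA-approved dosing point to a source that the documents do not reproduce. They also introduce both schedules, so they cannot choose between them.

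Appendix G does not help either. Its code is not this study's number (UH IRB# 07-17-33, Amgen 20207105), and its label is Week 16, whereas the titration cards are dispensed at Week 0. As extracted, its rows fit neither schedule. I place no weight on their content, because the table may be damaged.

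**The case against.** The strongest reply is that this is small. The schedules agree on Day 1 and from Day 6, the difference is 0.6% of the prescribed total over 112 days, and no sample size, endpoint, test or analysis set depends on it. In a single-arm pilot with a Week 16 endpoint, the conclusion is not threatened. All of that stands, and I claim no bias in the primary analysis. It limits the consequence, but it does not remove two contradictory study-drug instructions.

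A second reply is that subjects dose from a labelled card and staff go through its printed instructions with them, so a working reference exists in practice. That is fair: one uniform card would give uniform dosing, and compliance could be checked against it. But the label text is not in the documents, and whichever schedule the card carries, it departs from one protocol page on Days 2 to 5. The limited statement, that a first-week deviation cannot be judged against the protocol as written, therefore holds.

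Two points of wording should also be granted. The code on the Appendix G page is not this study's, but the documents do not say what it identifies. The tablet mix rests on one tablet per dose; the difference in milligram totals does not.

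**Conclusion.** The contradiction is real and nothing in the documents resolves it. The two schedules differ on each of Days 2 to 5, by 10 mg a day and 40 mg in all, which is 26.7% over Days 1-5 and 14.8% over Days 1-7 relative to the Summary. Full maintenance dosing starts on Day 6 in one and on Day 5 in the other.

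The result rests on reading the two schedules as printed, with Day 5+ taken to include Day 5. It does not rest on Appendix G. No claim is made that subjects received different doses or that the Week 16 result is affected. It still has to be corrected, because it is an instruction for giving the study drug, and the protocol's rules on deviations, overdose and non-compliance need one dose per day to refer to. I take no view on which schedule is right.

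**What to change.** The sponsor should:

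1. Confirm the intended titration and state it in one table, with the Summary, Section 1.4 and Section 7.1.2 all referring to it. The Section 1.4 sentence on the length of titration should agree with that table.
2. Replace the Appendix G page with the card layout used in this study, and correct the Appendix N reference in Section 7.1.1.
3. Reconcile the Section 7.1.3 statement that all drug is supplied in bottles with the titration cards in the Summary and in Sections 7.1.1 and 7.1.2.
4. Check that the card, the pharmacy instructions and the subject instructions match the single table.

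The cost is a protocol amendment and that check. It adds no patients, visits or procedures, and the statistical analysis does not change.

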1. INTRODUCTION

1.1. Apremilast

Apremilast (Otezla) is an oral agent that modulates multiple inflammatory pathways through targeted phosphodiesterase type 4 (PDE4) enzyme inhibition. It is used for the treatment of inflammatory autoimmune disorders, such as psoriatic arthritis and psoriasis that involve elevated cytokine levels.

PDE4 is one of the major phosphodiesterases expressed in leukocytes. Inhibitors of PDE4 cause accumulation of intracellular cyclic adenosine monophosphate (cAMP), resulting in inhibition of pro-inflammatory cytokine transcription and other cellular responses such as neutrophil degranulation and chemotaxis.

1.2. Psoriasis

Disease significance: The prevalence of skin disease exceeds those of obesity, hypertension or cancer. One in three Americans suffers with a skin disease, and ~2-3% of these individuals have psoriasis. Costs of treating these patients are believed to exceed \$1B, including over \$350M in prescriptions alone [1-5]. Chronic inflammation in psoriasis is often not limited to the skin, as evidenced by a high frequency of other significant co-morbidities including psoriatic arthritis, inflammatory bowel disease, lymphoma, obesity and metabolic syndrome [6-8], and recent evidence indicates that psoriasis patients have increased risk of developing and dying of cardiovascular diseases (CVD) [9]. Psoriasis patients also experience increased emotional burden via increased depression, mood disorders and suicidal ideation [10], an impact which may be purely from reactions to disfigurement, but which may also be a result of sensors in the brain of distant (skin) inflammation. Intervention at several points during the inflammatory disease cycle of psoriasis has revolutionized the understanding of psoriasis, and can produce clinical resolution in many, but not all patients. Improving understanding of psoriasis benefits not only the quality of life for patients with psoriasis, but also other inflammatory diseases of skin and other organs, as drugs initially developed for psoriasis have been extended to other indications. In particular, work that can be leveraged to other conditions remains to be done in unraveling the complex systemic interactions involving neurologic, immunologic, genetic, cellular and cutaneous biology responsible for the inflammatory responses in other organ systems when initiated by the skin of active psoriasis, or cutaneous GVHD, or dermatitis [11]. Toward that end, improved understanding of psoriatic inflammation progressively moved treatment upstream from broad immunologic suppression (i.e., cyclosporine or steroids) to somewhat more targeted but still fairly broad approaches (LFA-3-FcIgG, anti LFA-1, TNF inhibitors), to upstream Monocyte/Dendritic cell cytokine-initiated pathways (i.e., IL-12 p40, IL-23, PDE4) that drive a highly specific T cell lineage (Th17) mediating skin psoriasis.

CELLULAR COMPONENTS

Monocytes: Monocytes (Mon's) and their derived subpopulations are highly plastic and sensitive sentinels of inflammation. They play a critical role in psoriasis, are extremely strong candidates for mediating aspects of co-morbidities associated with psoriasis, and appear to be useful as biomarkers of Framingham Risk associated with psoriasis. However, there is extremely limited understanding of how Mon's respond to the chronic inflammatory stimuli they encounter either as developing precursors in the bone marrow (BM) or upon egress into circulation and interaction with the activated endothelium of a psoriatic lesion. Distinct circulating Mon populations arise from a common granulocytic-macrophage myeloid precursor in the BM, and have been genotyped; classical

monocytes (Mon-1, CD14⁺⁺ CD16^{neg}), intermediate monocytes (Mon-2, CD14⁺⁺ CD16⁺) and non-classical monocytes (Mon-3, CD14⁻ CD16⁺⁺) [12-18]. It is believed that Mons do not proliferate in circulation and reconstitution of the Mon pool is accomplished through maturation of a common BM-derived common myeloid progenitor. Mon-1s comprise the majority of circulating Mons that interact with endothelial cells (EC) and plasma proteins for approximately 1-3 days [19, 20], and then traverse the endothelium and enter tissue. Initial Mon-1 binding to EC are postulated to result in two potential outcomes; 1) **cells that adhere and extravasate** directly into surrounding tissue are likely to differentiate into macrophages and/or dendritic cell subsets, and 2) Mon-1 **cells that do not extravasate**, but transiently interact with endothelia and release, triggering transition to Mon-2 intermediate cells.

Among the Mon subsets [12-18] Mon-2s have been reported to produce elevated levels of TNF α upon challenge, and exhibit reduced levels of IL-10 production--they have therefore been identified as pro-inflammatory. Mon-2 are also the main producers of reactive oxygen species (ROS) [16] and secrete pro-atherogenic micro-particles (MP's) (also elevated in psoriasis) [21, 22]. Indeed, myeloperoxidase (MPO) is elevated in psoriasis serum and appears derived from tissue Mon's/macrophages [23]. Activated Mon-2 cells also exhibit high levels of the angiogenic factors ENG and Tie2 (TEK), and appear upregulated for trans-endothelial migration to tissue via CCR2, CX3CR1, CXCR4, and ICAM-1 receptors [16]. They demonstrate enhanced antigen processing, and can be precursors to tissue macrophages, dendritic cells and other professional antigen presenting cells that initiate and direct T cell mediated response to antigenic challenge. Mon-2's also express the highest level of the toll-like receptor 4 (TLR-4) [24, 25] for which a number of endogenous ligands are overexpressed in psoriasis (i.e., EDA fibronectin, S100 A8/9/12) [26, 27].

Circulating Mon-2 cells are biomarkers of inflammation in numerous diseases [28-35], and are validated predictive biomarkers of cardiovascular disease (CVD) events [36], including myocardial infarction and death [24, 37, 38]. Indeed, psoriasis patients have elevated levels of circulating CD16⁺ cells, which contain the Mon-2 population [29, 39], and we and others have shown that Mon-2s are elevated in a subset of psoriasis patients [29, 39, 40]. We also discovered, in addition to elevations of Mon-2's that Mons in psoriasis are more highly aggregated and can carry adherent platelets. These self-aggregated Mons exhibit a differential transcriptional profile from other singlet Mon populations [40].

Skin inflammation, most explored in psoriasis, but also apparent in GVHD, dermatitis, and skin injury, appears to be detected by distant cells of the myeloid lineage, with clinical functional consequences. Monocytic cells are designed to be sensors of inflammatory perturbations, and have the capability to differentiate down multiple pathways, as appropriate to the signals. Their timing is intermediate between neutrophils and lymphocytes (3-14 days in circulation), and as such are very attractive candidates for giving us a practical "smoking gun" regarding recent signals that have been received, as well as giving us a handle on what type of effector functionality has been triggered.

